3.5. DRUG UNDER EVALUATION. BLINDING AND RELABELLING OF THE MEDICATION

The investigational medicinal product (IMP) is dapagliflozin 10 mg given once daily (film coated tablets, oral use).

The comparator will be placebo matching dapagliflozin 10 mg.

Either dapagliflozin or placebo will be administered through out the planned intervention period of the study (12 weeks).

AstraZeneca will donate both dapagliflozin 10 mg and placebo resembling dapagliflozin 10 mg for the study.

Identity of investigational product(s)

Investigational product	Dosage form and strength	Manufacturer
Dapagliflozin	10 mg, Green, plain, diamond shaped, film coated tablet (orally)	AstraZeneca
Matching placebo for dapagliflozin	Green, plain, diamond shaped, film coated tablet (orally). Does not contain active ingredient	AstraZeneca

Primary packaging of the Investigational Medicinal product (IMP) will be carried out by AstraZeneca or their designee in accordance with Good Manufacturing Practice (GMP).

Unlabeled bottles (identical) containing 35 tablets of each IMP will be provided by AstraZeneca.

The tablets contain lactose, which may cause discomfort in lactose-intolerant individuals.

Label, storage and distribution are a promotor's responsibility.

Preparation and labelling of Investigational Medicinal Product

To allow for adequate treatment for the diabetes, only participants will be blinded to the treatment they receive. Attending physicians will know the group in which every patient is. To preserve blinding for the patient, the study medication (active and placebo) will be sent from AstraZeneca to a certified company (LogistaPharma), where, in coordination with the CRO of the study [ODDS, S.L.], it will be counted, labeled and distributed to the participating centers. The IMPs will be labelled in accordance with Good Manufacturing Practice (GMP) and local regulatory guidelines for labeling. The labels will fulfill GMP Annex 13 requirements for labelling.

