3.6. DRUGS NOT PERMITTED DURING THE CLINICAL TRIAL

While in the clinical trial, this protocol does not permit the use of the following drugs and/or changes in medication:

- Loop diuretics.
- SGLT2 inhibitors.
- Pioglitazone

If the attending physician considers that for the best care of the patient the use of any of the above mentioned drugs or changes in treatment is absolutely essential, the patient will be withdrawn from the study, the blinding for the patient will be broken and the promotor informed.

Any other change in medication which does not lead to withdrawal from the study will be recorded in the CRD.

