3.8. END POINTS

Primary: Changes in mean nocturnal BP from baseline (week 0) to last visit (week 12).

Secondary:

- Changes in office BP from baseline (week 0) to last visit (week 12).
- Changes in HbA1C from baseline (week 0) to last visit (week 12).
- Changes in albuminuria from baseline (week 0) to last visit (week 12).
- Natural variability of mean nocturnal BP on separate visits (placebo group).

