3.9. VISITS, VARIABLES AND MEASUREMENTS

Four clinical visits are planned in every patient at 0 (recruitment and randomization), 4, 8 and 12 weeks. Information on personal and family history of disease, clinical examination (including office BP determination), ABPM and blood and urine samples will be obtained on visits 0. The variables measured in the blood and urine samples depend on the criterium of the attending physician. For this trial, only HbA1c, serum creatinine, estimated glomerular filtration rate (eGFR) and albuminuria are mandatory. All this information, except personal and family history of disease, will also be collected at week 12 (see “3.20. Conduct of the study”). Thirty days after the end of the medication (visit of week 12) all participants will be contacted by telephone to assess safety. For the initial laboratory data required in the CRF, data obtained in primary care in the previous 3 months could be valid. These data will be repeated at the end of the study. Informed consents for the study will be signed by the patients before coming to the hospital. Blood samples extractions included in this protocol will be done, handled and analyzed at each clinical setting according to usual clinical

practice. No blood sample storage will be needed in this study. Extra blood samples drawn will be handled as described in “3.23. Addendum”.

The relationship of the procedures performed at every clinical visit is presented below (see “3.20. Conduct of the study”). Case report forms (CRFs) are presented in Annex I. Albuminuria will be measured according to generally used and previously described methodologies(18-23).

ABPM will be measured using Mobil-o-Graph that will give us 24 hours brachial and central BP as well as pulse wave velocity and heart rate(24). As diary of activity of the patient will not be recorded, in this study, nocturnal (or nighttime) blood pressure refers to measurements within the period from 12.00 p.m. to 6.00 a.m.

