3.10. WITHDRAWAL OF PATIENTS FROM THE STUDY AND UNBLINDING

Any patient can be withdrawn from the study at anytime during follow-up based on medical criteria of attending physician. The latter will detail the reasons of the withdrawal and communicate it urgently to the coordinating office of the trial if needed. If the reason for withdrawal is an adverse event (AE), the patient will be followed according to the procedures described for AEs (3.16).

Any patient can decide to abandon the study at any time during the study.

Withdrawal from the trial for any reason is definitive. When leaving the study, the main reason will be recorded and, if possible, the patient should have a final exam with the content of the visit of week 12. Patients that abandon the study will not be substituted.

All the above mentioned situations cause unblinding of the study. The primary care physician is always aware of the medication that receives the patient (single blind) and

will be the contact person and responsible to break the blind. Contact details are available in the patient information form. After unblinding, the responsible primary care physician will report it to the coordinating office of the project (ODDS, S.L., [contact]).

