3.13. PLAN OF ANALYSIS

The main analysis will compare baseline and final visit values of nocturnal blood pressure and all the rest of quantitative variables of interest within each stratum of albuminuria by means of paired t-test. Changes of nighttime blood pressure from baseline to final visit among patients with high and very high albuminuria levels will be compared to placebo with t-test.

Variables will be described by means of mean (and standard deviation) or proportion depending on the type of variable considered. Whenever the test of hypothesis may involve discrete variables, chi-squared test will be used.

Comparability of treatment and placebo groups will be tested (t-student or chi-squared test, depending on the variable) to assess randomization, and linear regression will be used to adjust for potential confounders, if needed; stratum of albuminuria at randomization will be forced in the model.

To respond to secondary objectives, the same analyses will be done for each stratum of albuminuria at randomization.

Only patients that complete the 3-month follow-up will be analyzed. Patients who do not complete the follow-up will be compared to those who adhere to the protocol.

No interim analysis is planned. A *p* value<0.05 will be considered as statistically significant.

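### Section 3.13 analyses completers only, with no all-randomised analysis, missing-data method or sensitivity analysis of the treatment effect, so the estimate compares those who stayed and not those randomised

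*Combined protocol and SAP*

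**What the plan says.** **Analysis set (3.13).** "Only patients that complete the 3-month follow-up will be analyzed". The only use made of the others is this: "Patients who do not complete the follow-up will be compared to those who adhere to the protocol". Linear regression is available to adjust for confounders if needed, with albuminuria stratum forced in, but still among completers. No section defines an all-randomised set, an imputation or likelihood method, or a sensitivity analysis of the treatment effect. What counts as completing is not defined.

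**Who knows the arm, and who can withdraw patients.**
- 3.5: "Attending physicians will know the group in which every patient is".
- 3.10: "Any patient can be withdrawn from the study at anytime during follow-up based on medical criteria of attending physician".
- 3.6: if the attending physician judges a listed drug or a treatment change essential, "the patient will be withdrawn from the study, the blinding for the patient will be broken and the promotor informed". The same section adds: "Any other change in medication which does not lead to withdrawal from the study will be recorded in the CRD".

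**What is measured, and when (3.9, 3.20).** ABPM is done at visit 0 and week 12 only. Office BP is also taken at weeks 4 and 8. On the visit 0 measurements, which include ABPM, 3.9 says: "All this information, except personal and family history of disease, will also be collected at week 12". Section 3.10 asks that leavers have, where possible, an exam with week-12 content.

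**Code breaks.** Section 3.10 says withdrawals cause unblinding. Section 3.5 leaves it to the promotor, without criteria, to decide whether data from a patient whose code is broken are excluded.

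**Drop-out (3.11).** The expected rate is 9%, with SD 12 mmHg and a target difference of 5 mmHg.

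**The concern.** Randomisation makes the arms comparable at entry. An analysis set fixed by who is still present at week 12 can lose that comparability, because leaving may depend on treatment and on outcome together. Comparing leavers with adherers describes the drop-outs. It does not recover the effect in everyone randomised.

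In this single-blind design, the physician who may withdraw a patient knows the arm and sees office BP at weeks 4 and 8. Adverse events and patient choice are further routes out, and they need no unblinded physician. Nothing in 3.13 guards against any of them.

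At stake is whether the primary estimate means what a randomised comparison should mean. A second loss is that, as 3.13 reads, an exit ABPM obtained under 3.10 would not enter the treatment comparison.

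**Working it through.** **1. Reproduce the plan's sample size (inputs from 3.4 and 3.11).** Two-sided alpha 0.05, power 80%, difference 5, SD 12, ratio 2:1.
- Placebo evaluable: 1.5 × (12 × (1.960 + 0.842) / 5)² = 67.8, so 68; active 136.
- Divide by 0.91: 75 and 150, matching 3.11. Planned loss is 0.09 × 225 = 20.25 patients.
- Power at 136/68 is 80.1%. The sample size is sound, and the allowance replaces lost precision only.

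**2. Bias of a completers analysis.** Within an arm, completer mean − all-randomised mean = d × (completer mean − leaver mean), where d is the fraction leaving. The bias in the treatment difference is this quantity for active minus the same for placebo. It is zero if d and the gap are equal in both arms.

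**3. Illustration (a): unequal loss.** Assumed, not from the documents: 6% active and 15% placebo leave (150 × 0.06 + 75 × 0.15 = 20.25, the planned total), and patients with a worse BP change are more likely to leave, with correlation r.
- If the worst fraction d left outright (r = 1), the retained mean would shift by −12 × φ(z) / (1 − d), where z is the 1 − d normal quantile: −1.52 at 6% and −3.29 at 15%. The difference is 1.77.
- Bias = 1.77 × r: 0.53 at r = 0.3 and 0.89 at r = 0.5. Placebo loses more of its poor responders, so the bias is against dapagliflozin.
- Implied leaver-completer gaps (shift × r / d): 1.52 × 0.3 / 0.06 = 7.6 and 3.29 × 0.3 / 0.15 = 6.6 at r = 0.3; 12.7 and 11.0 at r = 0.5. That is about 7-13 mmHg, up to about one SD.

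Simulation, 40,000 trials, pooled t-test:

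| r | bias (mmHg) | two-sided type I error | power at 5 mmHg |
|---|---|---|---|
| 0 | 0.00 | 5.0% | 78.3% |
| 0.1 | 0.18 | 5.1% | 75.4% |
| 0.3 | 0.53 | 5.9% | 69.8% |
| 0.5 | 0.89 | 7.7% | 64.6% |

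The normal approximation without bias (141/64) gives 78.9%. With SE = 12 × √(1/141 + 1/63.75) = 1.81, the error for r = 0.3 to 0.5 splits into 4.8-7.1% false findings for placebo and 1.2-0.7% for dapagliflozin, the latter below the nominal 2.5%.

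**4. Illustration (b): equal loss, opposite gaps.** Assumed: 9% leave each arm, with gaps of 5 mmHg in opposite directions. Bias = 0.09 × 5 × 2 = 0.9 mmHg. SE = 12 × √(1/136 + 1/68) = 1.78. Type I error is 8.0%, of which 7.3% lies in the direction of the bias, and that direction could be either one.

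**5. Equal loss, equal relation to outcome.** With 9% in each arm and r = 0.3 or 0.5, bias is 0.00 and error 5.0% or 4.9%.

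**6. How far imputation helps.** A simplified check used 3,000 trials with 20 imputations from arm and office BP only, office BP known for all, 6%/15% leaving and an assumed office-nocturnal correlation of 0.6.
- If leaving follows office BP, bias falls from about 0.56 and 0.81 to within 0.1 mmHg of zero, and power rises from 70% and 65% to 80% and 79%.
- If leaving follows nocturnal BP itself (r = 0.3 and 0.5), bias falls only from 0.50 and 0.87 to 0.30 and 0.57, and power rises from 71% and 65% to 76% and 72%.

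Imputation removes only the bias that its predictors explain.

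**The case against.** The strongest reply has four parts.

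- *This is a 12-week pilot with 9% expected loss, and no bias has been demonstrated.* This stands as a limit on severity. It does not remove the point, because 3.11 powers a two-sided between-arm test and 3.13 applies a 0.05 threshold.
- *The unblinded-physician route is narrow.* This largely stands. No physician sees on-treatment nocturnal ABPM before a withdrawal, and 3.6 lets other medication changes simply be recorded. Illustration (a) is ordinary outcome-related drop-out and needs no knowledge of the arm. The physician's role adds to the risk, but the gap in 3.13 exists without it.
- *The bias figures come from outside the documents.* True. The unequal split, the correlations and the opposite-sign gaps are all assumptions.
- *A leaver with an exit exam might count as having completed.* Possible, since the term is undefined. However, 3.10 makes withdrawal definitive and 3.13 sets non-completers apart, so the natural reading leaves them out.

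A reader might infer that the plan is tilted towards a false finding for dapagliflozin. The documents do not support that. They give no direction, and in illustration (a) false findings for dapagliflozin become rarer. Nor does the point imply that the sample size is wrong; it reproduces exactly.

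**Conclusion.** The omission is established from the text: completers are the only analysis set, and nothing in the plan protects the between-arm estimate against drop-out that differs by arm. Confidence in this is high.

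Confidence in the magnitude is low. Under the assumed scenarios the bias runs from zero to about 0.9 mmHg against a 5 mmHg target. In the unequal-loss case the main harm is lost power, and at r = 0.1 it is small. In the opposite-gap case it is a type I error of about 8%.

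This should be fixed before analysis. It does not show that the trial's result would be wrong.

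**What to change.** **In 3.13, state:**

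> The primary between-arm comparison of change in mean nocturnal systolic BP from baseline to week 12 includes all randomised patients in their assigned arm. Missing week-12 values are multiply imputed from arm, baseline nocturnal BP, albuminuria stratum, hospital and available week 4 and 8 office BP, itself imputed when missing. Sensitivity analyses: exit ABPM as the final value; delta-adjusted (tipping-point) imputation; completers only. The same all-randomised rule applies to the between-arm comparisons of office BP, HbA1c and albuminuria.

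Points to settle with it:
- Systolic is the measure named in 3.11; 3.8 says only mean nocturnal BP.
- Exit ABPM should not be an imputation predictor. Leavers have no week-12 ABPM and completers have no exit ABPM, so the relation between the two cannot be estimated from the trial.
- Keep the existing completers sentence, but limit it to the within-group paired t-tests. Every analysis then has a stated population.
- State that the imputation estimates the effect as if leavers had continued like similar patients in their arm. The exit-ABPM and tipping-point analyses cover departures from that.
- State that a code break alone is not a reason to exclude data, and reconcile 3.5, 3.10 and 3.13. Otherwise the promotor's discretion in 3.5 could undo the all-randomised rule. No change to the withdrawal rules is proposed.

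**Cost.** The change needs wording and modest analysis work; the exit exam and the week 4 and 8 office BP are already planned. The result would rely on an imputation model for about 20 patients at the planned loss, and early leavers may have no on-treatment office BP.

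If leavers in fact carry no treatment effect, the overall effect is 5 × 0.91 = 4.55 mmHg. An analysis targeting that effect, which is a different quantity from the one imputed above, has 72.3% power with information from 136/68 only and 76.5% if all 225 supply final values. If all 225 supply values and the effect stays at 5 mmHg, power is 83.8%.

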3.4. RANDOMIZATION

Two strata will be considered based on albuminuria levels:

- High albuminuria (30-300 mg/g creatinine)
- Very high (>300 mg/g creatinine)

Patients will be randomized to either dapagliflozin or placebo in a 2:1 ratio.

Figura 2.-Randomization scheme

Total number of patients: 225; distributed as:

- 150 diabetic patients treated with dapagliflozin (10mg/day in a single dose), half of them with high albuminuria levels (albuminuria 30-300 mg/g of creatinine) and half with very high albuminuria levels (albuminuria > 300 mg/g of creatinine)

- 75 diabetic patients treated with placebo, half of them with high albuminuria levels (albuminuria 30-300 mg/g of creatinine) and half with very high albuminuria levels (albuminuria > 300 mg/g of creatinine)

Randomization will be stratified by albuminuria strata and participating hospital (three hospitals); center specific randomization lists (active treatment or placebo) will be prepared centrally at the project office with a treatment code assigned to each patient.

Allocation will be concealed by means of sequentially numbered, opaque, sealed envelopes that contain the medication code assigned. The envelopes have to be opened sequentially and only after the participant's name is written on the appropriate envelope.

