3.11. SAMPLE SIZE CONSIDERATIONS

For the main objective of the study, changes in mean nocturnal systolic blood pressure will be compared between the active treatment and placebo groups.

The use of SGLT2 inhibitors has been reported to be associated with reductions in office blood pressure of 4–8 mmHg, reductions that could be even higher with the use of ambulatory BP monitoring.¹⁵

Accepting an alpha error of 0.05 in a two-sided test, 150 patients are needed in the active treatment group and 75 in the placebo group (2:1 randomization) to have an 80% power (beta error=0.2) to detect as statistically significant a difference greater than or equal to 5 mmHg in mean nocturnal BP between placebo and active treatment (conservative estimate of the expected effect). The standard deviation is assumed to be 12 mmHg and it is expected a drop-out rate of 9%.

In the prespecified subgroup analysis by albuminuria levels, this sample size (75 in active treatment and 37 in placebo) allows to detect as statistically significant, within each albuminuria stratum and with the same assumptions and alfa and beta errors, a difference greater than or equal to 7,1 mmHg in the reduction of mean nocturnal BP between both groups (active treatment and placebo), an effect still within what can be expected.

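### The overall nocturnal BP comparison is primary at 5%, but section 3.13 calls within-stratum paired tests the main analysis and puts no testing order or alpha control on the two stratum comparisons

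*Combined protocol and SAP*

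**What the plan says.** Section 2 lists the overall comparison of change in nighttime BP as the primary objective. The same comparison within the high and very high albuminuria strata appears as the first two secondary objectives.

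Section 3.11 sizes the trial on the overall comparison: "Accepting an alpha error of 0.05 in a two-sided test", the trial is "to have an 80% power (beta error=0.2") for "a difference greater than or equal to 5 mmHg in mean nocturnal BP between placebo and active treatment". It then describes the strata as a prespecified subgroup analysis and gives each one the same alpha and beta, with a detectable difference of 7.1 mmHg.

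Section 3.13 opens by labelling paired baseline-to-final t-tests within each stratum as the main analysis. The between-arm sentence follows: "Changes of nighttime blood pressure from baseline to final visit among patients with high and very high albuminuria levels will be compared to placebo" by t-test. Later it adds: "To respond to secondary objectives, the same analyses will be done for each stratum of albuminuria at randomization". The section ends with one rule for every test, that a p "value<0.05 will be considered as statistically significant". No order of testing, gate or adjustment is written anywhere.

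**The concern.** The same variable is compared between arms three times: overall, in the high stratum and in the very high stratum. Each comparison has the full 0.05. Sections 2 and 3.11 rank these tests, but a rank is not a testing rule. The plan does not say how to treat a stratum with p<0.05 when the overall test has failed. Under section 3.13 that stratum result is simply statistically significant.

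Section 3.13 also undercuts the rank by placing the main analysis inside the strata. It does so with a paired test, which makes no comparison with placebo. Someone working from section 3.13 alone could present a stratum result, or even a within-arm change, as the main finding. At stake is which p-values may support the claim that dapagliflozin lowers nighttime BP.

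**Working it through.** **Inputs.** Two-sided alpha 0.05, power 80%, difference 5 mmHg (section 3.11). SD and dropout: "The standard deviation is assumed to be 12 mmHg and it is expected a drop-out rate of 9"% (section 3.11). Allocation: "Patients will be randomized to either dapagliflozin or placebo in a 2:1 ratio" (section 3.4). Strata of equal size (section 3.4).

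**1. The plan's own figures.**
- Placebo n = (1 + 1/2) × 12² × (1.960 + 0.842)² / 5² = 67.8, so 68; active 2 × 68 = 136.
- Dividing by 0.91 gives 74.7 and 149.5, so 75 and 150. This matches the stated 225.
- Per stratum after 9% dropout: 75 × 0.91 = 68.25 and 37 × 0.91 = 33.67. Detectable difference = 2.802 × 12 × √(1/68.25 + 1/33.67) = 7.08 mmHg, matching the stated 7.1.

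So both the overall test and each stratum test are planned at the full two-sided 0.05.

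**2. Error across the three between-arm tests, no effect anywhere.** Let Z₁ and Z₂ be the stratum statistics. They are independent because no patient is in both strata. With equal strata the overall statistic is Z = (Z₁ + Z₂)/√2, which has correlation 0.707 with each stratum. With c = 1.96,

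P(at least one |Z| > c) = 1 − ∫ from −c to c of φ(x)[Φ(min(c, √2c − x)) − Φ(max(−c, −√2c − x))] dx = 0.1150.

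| Event under no effect | Probability |
|---|---|
| Overall test significant | 5.0% |
| A stratum significant, overall not | 6.5% |
| At least one of the three (sum of the two rows above) | 11.5% |
| At least one of the three in favour of drug | 5.8% (nominal 2.5%) |

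Checks:
- The two strata alone give 1 − 0.95² = 9.75%. Three independent tests would give 1 − 0.95³ = 14.3%. The result lies between these.
- Simulating actual t-tests (200,000 trials, 68 vs 34 per stratum) gives 11.6% for any of the three and 5.9% in favour of drug.
- Unequal strata change little: 11.4% at 70:30 and 10.8% at 90:10.

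**3. Effect of a gate** (a stratum counts only if the overall test is significant). If both strata are null, the overall test limits the error to 5%. If one stratum is null and the other is not, only the null stratum's own test can err, again at no more than 5%. The gate therefore holds the error across the three tests at 5%.

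**4. Power cost of the gate.** With 68 vs 34 per stratum, SE = 12 × √(1/68 + 1/34) = 2.52 mmHg.
- *5 mmHg in both strata.* Expected Z per stratum is 5/2.52 = 1.98, and overall 1.98 × √2 = 2.81. Overall power is about 80%, gate or no gate. Stratum power is about 51% ungated and 49% gated.
- *7.1 mmHg in one stratum, none in the other.* Expected Z in the responding stratum is 7.1/2.52 = 2.82, and overall 2.82/√2 = 1.99. Power in the responding stratum is about 80% ungated. The overall test passes only about 51% of the time, so gated power is about 49%.

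**The case against.** The strongest reply is that the plan already ranks its tests. Sections 2 and 3.11 make the overall comparison primary, and section 3.13 itself assigns the stratum analyses to secondary objectives. A reader might infer that the three tests are unranked and that the false-positive rate of the primary comparison is 11.5% instead of 5%. The documents do not support that. The overall test keeps its 5%, and no passage allows success to be declared on any one of the three. This part of the reply stands, so the 11.5% is conditional.

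The between-arm sentence in section 3.13 may also describe the pooled population, since every eligible patient is in one stratum or the other. On that reading it is the primary test. This is fair, but the sentence can equally be read stratum by stratum, and that ambiguity needs removing.

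A reader might also add office BP, HbA1c and albuminuria in each stratum and arrive at 30–35% for at least one false positive in nine tests. That figure needs assumed between-endpoint correlations (0.5 to 0). It also mixes different secondary claims: a chance finding on HbA1c would not be read as a nighttime BP effect. It should not be used.

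Finally, the study is called a pilot, and the two strata are prespecified and used in the randomization. That lowers the stakes. It does not settle the matter, because section 3.11 powers a formal hypothesis test and presents the strata as able to yield statistical significance.

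**Conclusion.** The point holds in a limited form. The primary comparison is identified and its type I error is 5%. What is missing is any testing order or alpha control for the two secondary stratum comparisons. In addition, the main-analysis sentence in section 3.13 conflicts with sections 2 and 3.11.

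If any of the three between-arm tests could support the nighttime BP claim, the chance of at least one false positive is 11.5% two-sided, or 5.8% in favour of drug. In 6.5% of null trials a stratum would be called significant beside a non-significant overall result. These figures assume no effect in either stratum, equal strata and unadjusted tests. They leave out the paired within-stratum tests and any adjusted regression, which fall under the same p<0.05 rule.

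This does not invalidate the primary inference. It should be corrected because it leaves open which result on the primary variable counts.

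**What to change.** Replace the main-analysis sentence in section 3.13, so that it does not remain beside the new text, with:

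> The primary analysis is the overall dapagliflozin-placebo difference in change in nocturnal systolic BP, tested at two-sided 0.05. The two albuminuria-stratum comparisons are secondary; they may be called statistically significant only if the overall test is, and are otherwise reported as estimates with 95% CIs.

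Reword the between-arm sentence that follows so that it agrees. State that office BP, HbA1c and albuminuria are secondary and carry no multiplicity control. Significance statements for them need not be banned.

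**Cost.** A short text change and no extra patients. Overall power is unchanged. The price falls on the strata: about two percentage points under a uniform 5 mmHg effect (51% to 49%), but about thirty points if a 7.1 mmHg effect is confined to one stratum (80% to 49%). If the sponsor thinks an effect in one stratum only is plausible, it should accept that loss knowingly. An alternative that also gives 5% across the three tests is a common level of about 0.0205 for each, but the overall test would then no longer have its full 0.05.
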